### 7.11.3 Vital Signs

Descriptive statistics for body weight and vital signs (oral temperature, respiratory rate, systolic and diastolic blood pressure, and pulse rate) and changes from baseline values at each visit will be presented by treatment group for the Treatment Period and by treatment sequence for the Treatment-RW period. The End of Treatment is the last non-missing postbaseline value in the Treatment Period; End of study is the last non-missing postbaseline value.

Vital sign values will be considered PCS if they meet both the observed-value criteria and the change-from-baseline criteria listed in [Table 7.11-3](#). The number and percentage of patients with postbaseline PCS vital signs will be tabulated by treatment group for the Treatment Period and by treatment sequence for the RW Period and the Treatment-RW Period. The percentages will be calculated relative to the number of patients with nonmissing baseline values and at least 1 assessment in the corresponding postbaseline period. A supportive listing of patients with postbaseline PCS values will be provided, including the PID number, trial center, and baseline and postbaseline values.

A listing of all AEs for patients with PCS vital sign values will also be provided.

**Table 7.11-3 Criteria for Potentially Clinically Significant Vital Signs**

Parameter	Flag	Criteriaa	
		Observed Value	Change From Baseline
Sitting systolic blood pressure, mm Hg	High	≥ 180	Increase of ≥ 20
	Low	≤ 90	Decrease of ≥ 20
Sitting diastolic blood pressure, mm Hg	High	≥ 105	Increase of ≥ 15
	Low	≤ 50	Decrease of ≥ 15
Sitting pulse rate, bpm	High	≥ 120	Increase of ≥ 15
	Low	≤ 50	Decrease of ≥ 15
Weight, kg	High	—	Increase of ≥ 7%
	Low	—	Decrease of ≥ 7%

a A post-baseline value is considered potentially clinically significant if it meets both the observed-value and the change-from-baseline criteria.

bpm = beats per minute.

## 7.11.4 Other Safety Parameters

### 7.11.4.1 Physical Examination

Any physical examination abnormality that the investigator considers to be potentially clinically significant and changed from the baseline will be reported as an AE. No separate analysis for Physical Examinations is planned.

## 7.12 HEALTH OUTCOMES ANALYSIS

Health outcome analyses will be performed on the ITT population for the Treatment Period and on the RW Population for the RW Period.

### 7.12.1 Irritable Bowel Syndrome–Quality of Life Assessment (IBS-QOL)

The IBS-QOL parameters consist of the overall average score and eight subscale scores (ie, dysphoria, interference with activity, body image, health worry, food avoidance, social reaction, sexual, and relationships). For the Week 12/ETP Visit and the Week 16/EOT Visit, change from baseline in the IBS-QOL overall average score and the subscale scores will be analyzed using an ANCOVA model with fixed effect terms for treatment group and geographic region and the corresponding baseline IBS-QOL score as a covariate.

**Table 7.12-1 Irritable Bowel Syndrome–Quality of Life Questionnaire**

Endpoint (Subscale)	Items		
Dysphoria (DY)	1, 6, 7, 9, 10, 13, 16, 30		
Interference with activity (IN)	3, 18, 19, 22, 27, 29, 31		
Body image (BI)	5, 21, 25, 26		
Health worry (HW)	4, 15, 32		
Food avoidance (FA)	11, 23, 28		
Social reaction (SR)	2, 14, 17, 34		
Sexual (SX)	12, 20		
Relationships (RL)	8, 24, 33		
Overall (OV)	All items		

Subscales are scored through simple summative scaling. All items are negatively framed (on a 1-5 point scale), with the highest response scale equaling the worst quality of life. When scored, all items are reversed so that, as IBS-QOL scores increase, quality of life increases. All final raw scores are transformed to a 0-to-100 scale using the following formula:

$$\text{Scale Score} = \frac{\text{Sum of the items} - \text{lowest possible score}}{\text{possible raw score range}} \times 100$$

This transformation converts the lowest and highest possible scores to 0 and 100, respectively. Scores between these values represent the percentage of the total possible score achieved.

If a patient is missing any item in the derivation of a subscale, that subscale is considered missing. If any item is missing, the total score is considered missing. However, the subscales with nonmissing items can still be calculated.

### **7.12.2 CDC Healthy Days Core Module (CDC HRQOL-4)**

The CDC HRQOL-4 (the Healthy Days Core Module) consists of 4 questions. Self-rated general health, physically unhealthy days, mentally unhealthy days, and poor physical/mental days are collected. Unhealthy days is defined as:

Unhealthy days = minimum of (physically unhealthy days + mentally unhealthy days, or 30)

Descriptive summaries for the derived unhealthy days and the change from baseline will be summarized descriptively at each visit. For the Week 12/ETP Visit and the Week 16/EOT Visit, treatment difference between the change from baseline score will be performed using ANCOVA model with fixed effect terms for treatment group and geographic region and the corresponding baseline measure as a covariate.

**8.0**

**CHANGES FROM ANALYSES PLANNED IN THE PROTOCOL**

## **9.0 DATA HANDLING CONVENTIONS**

### **9.1 VISIT TIME WINDOWS FOR SAFETY ANALYSIS**

Table 9.1-1 below presents the visits assigned for the safety analysis corresponding to the range of trial days (window) during which an actual visit may have occurred.

**Table 9.1-1 Visit Time Windows for Safety Analysis**

Derived Visit	Scheduled Test / Visit Daya	Window
Baseline	Day 1	Days $\leq$ 1
Week 4 (Day 29) Visit	Day 29	Days [2, 43]
Week 8 (Day 57) Visit	Day 57	Days [44, 71]
Week 12 (Day 85) Visit	Day 85	Days $\geq$ 72 but prior to RW Day 1
End of Treatment Period b	End of Treatment Period Visit	
Week 16 (RW Day 29) Visit	RW Day 29	Days $>$ RW Day 1
End of Trial	End of Trial Visit	

a Relative to the date of randomization or first RW dose; Day 1 = the day of randomization; RW Day 1 = the day of first RW dose.

b “End of Treatment Period/End of Trial” will be presented in analysis tables for safety parameters, including ECG, clinical laboratory, and vital signs.

Test/Visit Day will be calculated as follows: test/visit date – date of randomization or date of first RW dose + 1.

If there are multiple values available for the same Visit, the data with the latest date for that visit will be utilized for summary.

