The investigator must review each laboratory report, document this review, and record any clinically relevant changes occurring during the trial in the AE section of the eCRF. The laboratory reports must be filed with the source documents. All laboratory tests with abnormal values considered clinically significant during participation in the trial should be repeated until the values return to normal or baseline or are no longer considered clinically significant by the investigator or Medical Monitor. If such values do not return to normal/baseline within a period of time judged reasonable by the investigator, the etiology should be identified and the Sponsor notified. If laboratory values from non-protocol specified laboratory assessments performed at the institution's local laboratory require a change in patient management or are considered clinically significant by the investigator (eg, SAE or AE or study drug discontinuation), the results must be recorded in the eCRF.

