### 7.11.2 Clinical Laboratory Parameters

Descriptive statistics for clinical laboratory values (in SI units) and changes from the baseline values at each assessment time point will be presented by treatment group for Treatment Period and by treatment sequence for the RW Period. The End of Treatment is the last non-missing postbaseline value in the Treatment Period; End of study is the last non-missing postbaseline value. The hematology and chemistry laboratory parameters listed in Section 5.4.5 will be summarized.

Clinical laboratory test values will be potentially clinically significant (PCS) if they meet either the low or high PCS criteria listed in Table 7.11-2. The number and percentage of patients with postbaseline PCS clinical laboratory values will be tabulated by treatment group for the Treatment Period and by treatment sequence for the RW and Treatment-RW Periods. The percentages will be calculated relative to the number of patients with non-PCS baseline values and at least 1 assessment in the corresponding postbaseline period. A supportive listing of patients with postbaseline PCS values will be provided, including the PID number, trial center, and baseline and postbaseline values. A listing of all AEs for patients with PCS clinical laboratory values will also be provided. The PCS flags will be derived flags (not from the clinically significant laboratory tests reported as AEs by trial centers).

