## **9.5 REPEATED OR UNSCHEDULED ASSESSMENTS OF SAFETY PARAMETERS**

If a patient has repeated assessments prior to the start of double-blind study drug, then the results from the final non-missing assessment made prior to the start of the double-blind study drug will be used as baseline. If end-of-trial assessments are repeated or if unscheduled visits occur, the last non-missing post baseline assessment will be used as the end-of-trial assessment for generating summary statistics. However, all post-baseline assessments will be used for PCS value determination as described above and all assessments will be presented in the data listings.

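### Laboratory descriptive statistics take the latest or last value, so a repeat that ended on recovery, usually off drug, can replace the scheduled result at Week 16/End of Trial and in early stoppers

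*SAP*

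**What the plan says.** Three SAP rules decide which laboratory value is summarised.

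- SAP 9.1, note to Table 9.1-1: "If there are multiple values available for the same Visit, the data with the latest date for that visit will be utilized for summary".
- SAP 7.11.2: "The End of Treatment is the last non-missing postbaseline value in the Treatment Period". End of study is defined the same way, without the limit to that period.
- SAP 9.5, for repeated end-of-trial assessments or unscheduled visits: "the last non-missing post baseline assessment will be used as the end-of-trial assessment for generating summary statistics".

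Table 9.1-1 sets the windows: Days 2 to 43 for Week 4, Days 44 to 71 for Week 8, and from Day "72 but prior to RW Day 1" for Week 12. The Week 16 window is every day after RW Day 1, with no upper bound. No window refers to the last dose or to the withdrawal visit.

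Protocol 8.2.2 determines when repeats exist. It covers "All laboratory tests with abnormal values considered clinically significant during participation in the trial" and says that these "should be repeated until the values return to normal or baseline or are no longer considered clinically significant by the investigator or Medical Monitor".

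SAP 9.5 also contains a safeguard: "all post-baseline assessments will be used for PCS value determination as described above and all assessments will be presented in the data listings".

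**The concern.** Each rule is ordinary by itself. The difficulty is the combination. Under Protocol 8.2.2 a repeat exists because the previous result was abnormal, and repeating ends when the result has recovered or no longer matters. Taking the latest result then selects the record by its outcome, and always in the direction of recovery. With no cut-off after the last dose or the final visit, the selected record may also come from a patient who is no longer taking study drug, yet appear as a visit, End of Treatment or End of Trial result.

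At stake are the laboratory means, SDs, minima, maxima and changes from baseline in the affected rows. Exposure through early stopping may also differ by arm. Protocol 3.3 reports discontinuation for diarrhea of 5.3% on linaclotide and 0.4% on placebo in the two registration trials. At 300 per arm that is 300 × 0.053 ≈ 16 patients against 300 × 0.004 ≈ 1. How many of them would have an abnormal laboratory result is unknown.

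**Working it through.** The plan states no figure on this point, so there is none to reproduce. The check is a calendar exercise on Table 9.1-1, followed by an illustration of size with assumed inputs.

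**Inputs from the documents.** Chemistry and hematology are scheduled after baseline only at Week 12 (Day 85±3) and Week 16 (RW Day 29±3), per the Schedule of Evaluations. RW Day 1 is the day after the Week 12 visit (Schedule, note q). The last RW dose is usually RW Day 28 (SAP Table 9.2-1). Patients who withdraw have the EOT procedures, including laboratory tests, at discontinuation (Protocol 6.3). Planned size is 300 per arm.

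**Step 1: completers at Week 12.** RW Day 1 = visit day + 1, and the window ends the day before RW Day 1. Days left in the window after the visit = (visit day + 1) − 1 − visit day.
- Visit on Day 82: RW Day 1 is Day 83, 0 days left.
- Visit on Day 85: RW Day 1 is Day 86, 0 days left.
- Visit on Day 88: RW Day 1 is Day 89, 0 days left.

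If RW dosing starts as scheduled, a repeat on a later day cannot replace the Week 12 value. A repeat after RW Day 1 falls in the Week 16 window, where the scheduled Week 16 sample is normally later and supersedes it.

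**Step 2: Week 16/End of Trial.** Days from the usual last dose to the EOT visit = visit RW day − 28.
- RW Day 26: −2. RW Day 29: +1. RW Day 32: +4.

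A repeat prompted by the EOT sample comes later still, so it is generally off drug. The window has no end, so that repeat becomes the Week 16 value (SAP 9.1) and the End of Trial value (SAP 9.5).

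**Step 3: patients without an RW Day 1.** This group comprises patients who stop during the Treatment Period and completers who do not enter RW, whom the footnote to SAP Table 9.2-2 anticipates. Suppose, for illustration, an abnormal withdrawal sample on Day 75 and a normal repeat on Day 82. Both days are at least 72 and there is no RW Day 1 to close the window, so the Day 82 value is summarised as Week 12.

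The result differs when the two samples straddle windows. Day 40 lies in [2, 43] and Day 50 in [44, 71], so the Day 40 value stays in the Week 4 window and the Day 50 repeat falls in Week 8. Only End of Treatment would then change, if Day 50 counts as lying in the Treatment Period. SAP 7.11.2 does not settle that.

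**Step 4: unscheduled tests.** An unscheduled on-treatment test that is repeated within the same window is replaced by its repeat under SAP 9.1.

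**Step 5: size (assumed inputs).** Shift in arm mean = share of patients replaced × depth of the abnormality.
- Potassium, 1% to 3% of an arm, 0.8 to 1.0 mmol/L below baseline and recovering to it: 0.01 × 0.8 = 0.008 to 0.03 × 1.0 = 0.03 mmol/L.
- In SD units, 1% to 5% of an arm (3 to 15 of 300), values 2 to 4 SD from the mean replaced by average ones: 0.01 × 2 = 0.02 to 0.05 × 4 = 0.20 SD. For scale, the 95% half-width for a difference in means at 300 per arm is 1.96 × √(2/300) = 0.16 SD.

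The upper end needs 5% of an arm to have a 4 SD abnormality in one of the exposed positions, which is an extreme assumption. The minimum or maximum is more sensitive, because losing one extreme value can change it.

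**The case against.** The strongest reply is that the plan records the abnormal values elsewhere. All post-baseline results enter the PCS tables and every result is listed (SAP 9.5). Protocol 8.2.1.2.3 requires any laboratory abnormality judged clinically significant to be captured as an AE, which is also the condition for repeating it. A reader might infer that a value short of a PCS limit vanishes from all summaries. For example, at an assumed lower limit of normal of 3.5 mmol/L the potassium limit is 0.9 × 3.5 = 3.15, so 3.2 is not PCS. The documents do not support that inference: a 3.2 significant enough to be repeated should be an AE, and is tabulated as a TEAE when it meets the onset rules of SAP 7.11.1. This part of the objection stands and confines the harm to the descriptive rows.

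Two other broad readings also fail. One is that vital signs are affected in the same way. The latest-value rule applies to them, but neither document has them repeated until they recover, so the selection by outcome is missing. The other is that every window is biased. Step 1 excludes completers' Week 12 values, the main scheduled comparison with concurrent placebo, and no laboratory tests are scheduled at Weeks 4 and 8.

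One may add that SAP 9.2 ends a withdrawn patient's Treatment Period at the last dose, which would keep off-drug repeats out of End of Treatment. But that sentence sits among the efficacy windows, and Table 9.1-1 has no counterpart.

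Finally, the rule is prespecified, identical in both arms and purely descriptive, and last, first and worst value are all used as conventions. That is fair, but a last-value convention is neutral only if the existence of a later value does not depend on the earlier result. Here it does.

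**Conclusion.** The concern holds for laboratory descriptive statistics only. It affects three places: Week 16/End of Trial; End of Treatment and window values for patients who stop in the Treatment Period or never enter RW; and unscheduled tests repeated within one window. In each, the stated rules can replace an abnormal value with a recovered one, which in the first two is generally off drug.

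The effect on means is probably small (0.008 to 0.03 mmol/L for potassium under the assumptions above). The effect on minimum, maximum and SD is clearer but cannot be sized from the documents. PCS counts do not change. The conclusion assumes that repeats are carried out as Protocol 8.2.2 directs, that they enter the database, and that RW dosing starts on schedule. The documents do not show that the rule would hide electrolyte effects of diarrhea, and no such claim is made.

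**What to change.** In SAP 9.1, 9.5 and 7.11.2:

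1. For by-visit, End of Treatment and End of Trial laboratory descriptive statistics, use the scheduled-visit sample or, for patients who withdraw, the sample from the EOT procedures at withdrawal. If there are several, use the first valid one.
2. Exclude samples taken after the EOT or withdrawal visit from these summaries, which closes the Week 16 window and the windows of patients without an RW Day 1. State in SAP 7.11.2 whether a withdrawal-visit sample taken after the last dose counts as End of Treatment.
3. Keep all repeats for PCS determination and listings, as SAP 9.5 now has it.

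The repeat-testing rule in Protocol 8.2.2 is not touched. The cost is SAP wording and a small change to record selection in the programs. No new data are needed. The descriptive tables may look slightly less favourable.

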### **9.2 VISIT TIME WINDOWS FOR EFFICACY ANALYSIS**

Table 9.2-1 presents the analysis weeks assigned for the efficacy analysis of the patient diary data related to BM characteristics. These analysis weeks will be used in the calculations for all week-based parameters (e.g., Abdominal Score, SBM weekly frequency rate, BSFS weekly scores).

**Table 9.2-1 Analysis Time Windows for Efficacy Analysis**

Period	Analysis Week	Beginsa	Endsa
Pretreatment (Baseline b )	Week -2	Day -14	Day -8
	Week -1	Day -7	Day 1 (time of randomization)
Treatment	Week 1	Day 1 (time of randomization)	Day 7
	Week 2	Day 8	Day 14
	Week 3	Day 15	Day 21
	Week 4	Day 22	Day 28
	Week 5	Day 29	Day 35
	Week 6	Day 36	Day 42
	Week 7	Day 43	Day 49
	Week 8	Day 50	Day 56
	Week 9	Day 57	Day 63
	Week 10	Day 64	Day 70
	Week 11	Day 71	Day 77
	Week 12	Day 78	Day of last treatment period dose day c (usually Day 85)
RW	Week 1	RW Day 1	RW Day 7
	Week 2	RW Day 8	RW Day 14
	Week 3	RW Day 15	RW Day 21
	Week 4	RW Day 22	Day of last RW dose (usually day 28)

Note: There is no Day 0 or Week 0. For eDiary assessments in which a patient is asked to report if an event occurred “yesterday” or “today” (e.g., a bowel movement or rescue medication use), these windows pertain to when the event occurred, not to when the event is reported. For example, if a patient reports in eDiary on Day 78 a bowel movement occurring “yesterday,” that bowel movement (and subsequent stool consistency and straining scores) would be included in Analysis Week 11, not Analysis Week 12.

- a Relative to the date of randomization or first RW dose; Day 1 = the day of randomization; RW Day 1 = the day of first RW dose. For the calculation of rates (eg, stool frequency rates) in which the duration of a week or the overall period is calculated to the nearest hour, a day begins and ends at midnight.
- b Baseline values for efficacy parameters will be derived from the daily eDiary and eCRF data collected in the Pretreatment Period, specifically the period from 14 days before randomization up to the time of randomization.
- c For patients who fail to provide the date of last dose at the last visit, the later date of the last known dose (drug dispense eCRF) or the last eDiary date will be used to impute the last dose date.

For the Treatment Period or RW Period, diary day is calculated as diary date – date of randomization or date of first RW dose + 1. For the Pretreatment Period, diary day is calculated as diary date - date of randomization. However, the day of randomization is always trial Day 1. Patients will complete their diary entries once a day, with the exception of Day 1 of entry into the Treatment Period, during which 2 diary data sets will be collected. On Day 1, daily questions will be entered before and after the randomization, whereas weekly questions will be entered before but not after randomization.

If a patient withdraws during the Treatment Period or RW Period, the patient's Treatment Period or RW Period shall end on the day of the last dose. The affected Treatment Period or RW Period week shall be shortened to the end of the withdrawn patient's Treatment Period or RW Period, and all subsequent Treatment Period or RW Period weeks will be missing for that patient.

**Table 9.2-2** presents the analysis weeks assigned for the efficacy analysis of the patient diary data related to Weekly Questions (e.g., Weekly Patient Assessment of Constipation Severity, Weekly Patient Assessment of IBS Symptom Severity, Weekly Patient and Assessment of Adequate Relief, and Weekly Patient Assessment of Treatment Satisfaction).

**Table 9.2-2 Analysis Time Windows for Efficacy Analysis – Weekly Assessments**

Period	Analysis Week	Begins	Ends
Pretreatment (Baseline b )	Week -2	Day -11	Day -5
	Week -1	Day -4	Day 1 (time of randomization)
Treatment	Week 1	Day 7	Day 10
	Week 2	Day 11	Day 17
	Week 3	Day 18	Day 24
	Week 4	Day 25	Day 31
	Week 5	Day 32	Day 38
	Week 6	Day 39	Day 45
	Week 7	Day 46	Day 52
	Week 8	Day 53	Day 59
	Week 9	Day 60	Day 65
	Week 10	Day 66	Day 72
	Week 11	Day 73	Day 79
	Week 12	Day 80	Day of last treatment period weekly dose day (usually Day 84)*
RW	Week 1	RW Day 7	RW Day 10
	Week 2	RW Day 11	RW Day 17
	Week 3	RW Day 18	RW Day 24
	Week 4	RW Day 25	Day of last RW dose (28+3 Days)

\*For patients completing the treatment period, but not entering the RW period, Day 87 defines the End study day for Week 12 assignment.

In general, weekly questions will be assigned only to the analysis week for which the question covers at least 4 days of that week.

If a weekly question covers days from different study phases, the answers will be discarded. For example, a weekly question answered on study day 2 would cover part of 1 day from the treatment phase & 6 days from the pre-treatment phase, so these data would be discarded.

If patients answer the weekly questions multiple times for a week, for each question, the average of the respective answers will be assigned as the weekly value.

For time periods covering more than a week, the value will be calculated as the average of the weekly values. Thus, for pre-treatment, the value will be calculated as the average of week -2 and week -1.

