#### **7.5 SELECTION AND TIMING OF DOSE FOR EACH PATIENT**

All study drug will be administered orally once daily. Patients who meet all eligibility criteria at the Screening and Pretreatment Visits will be randomized to treatment (as described in Section 7.3) at the Randomization Visit (randomization number assigned by IWRS) and dispensed one bottle containing 35 tablets. Additional bottles will be dispensed at subsequent visits per the [Schedule of Evaluations](#). Patients will be instructed to take one capsule in the morning at least 30 minutes before breakfast. Patients will take their initial dose of study drug (one capsule) at the trial center during the Randomization Visit; patients must have fasted for at least 2 hours prior to arriving at the clinic for this visit. Patients will take study drug as usual in the morning before the Week 12/ETP Visit. Patients will be instructed to return all unused study drug and bottles to the study center at the visits defined in the [Schedule of Evaluations](#).

At the Week 12/ETP Visit, patients who have not withdrawn from the Treatment Period will be rerandomized by the IWRS (as described in Section [7.3](#)) and dispensed a bottle containing 35 tablets of double-blind study drug for the RW Period. Treatment will be taken according to the dosing instructions for the Treatment Period. Patients will take their initial dose of study drug in the RW Period (1 tablet) on RW Day 1 (ie, the day after the Week 12/ETP Visit).

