### **7.9.3 Additional Efficacy Endpoints**

Additional efficacy endpoints will be explored outside of the formal testing procedures and not controlled for multiplicity. These endpoints will include:

- 6/12 Week Abdominal Pain and Constipation (APC) +1 Responder

A 6/12 Week APC +1 Responder is a patient who meets the Weekly APC +1 Responder criteria for at least 6 out of the 12 weeks of the Treatment Period. For each week in the Treatment Period, a Weekly APC +1 Responder is a patient who has an increase from baseline of at least 1 in the respective CSBM weekly rate and has a decrease from baseline of at least 30% in the respective weekly abdominal pain score. If a patient did not enter information into the eDiary on at least 4 days for a particular Treatment Period week, the patient will not be considered a responder for that week.

- Change from Baseline in Abdominal Pain at Each Week

Abdominal pain is measured daily using an 11-point NRS. For each week on treatment, the weekly abdominal pain score is the mean of the non-missing daily values.

- Change from Baseline in CSBM Frequency Rate at Each Week

A patient's weekly CSBM frequency rate is the CSBM rate (CSBMs/week) calculated for that week.

- Change from Baseline in SBM Frequency Rate at Each Week

A patient's weekly SBM frequency rate is the SBM rate (SBMs/week) calculated for that week.

- Change from Baseline in BSFS (Stool Consistency) at Each Week

Stool consistency is measured using the 7-point BSFS. The patient's BSFS score for each week on treatment is the mean of the non-missing BSFS scores from the SBMs reported by the patient during the week.

- Change from Baseline in Stool Consistency at Each Week

Stool consistency is measured using a 5-point ordinal scale. The patient's stool consistency score for each week on treatment is the mean of the non-missing stool consistency scores from the SBMs reported by the patient during the week.

- Change from Baseline in Straining at Each Week

Straining is measured using a 5-point ordinal scale. The patient's straining score for each week on treatment is the mean of the non-missing straining scores from the SBMs reported by the patient during the week.

- Change from Baseline in Abdominal Discomfort at Each Week

Abdominal discomfort is measured daily using an 11-point NRS. For each week on treatment, the weekly abdominal discomfort score is the mean of the non-missing daily values.

- Change from Baseline in Abdominal Bloating at Each Week

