Treatment satisfaction is measured on a 5-point ordinal scale. Treatment satisfaction will be analyzed separately for each Treatment Period week.

- Adequate Relief

Assessment of adequate relief during the previous 7 days is measured on a binary scale (yes/no). Assessment of adequate relief will be analyzed separately for each Treatment Period week.

- 6/12 Week Adequate Relief Responder

A 6/12 Week Adequate Relief Responder is a patient who reports Adequate Relief for at least 6 out of the 12 weeks of the Treatment Period.

- Change from Baseline in Constipation Severity

Constipation severity is measured weekly using a 5-point ordinal scale. Change from baseline will be calculated at each week.

- Change from Baseline in IBS Symptom Severity

IBS symptom severity is measured weekly on a 5-point ordinal scale. Change from baseline will be calculated at each week.

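### SAP Table 9.2-2 cuts Week 9 to six days, so weekly answers on Days 66, 73 and 80 go to a week they do not mainly cover, against the SAP's own 4-day rule

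*SAP*

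**What the plan says.** SAP section 9.2 has two window tables. Table 9.2-1 defines the analysis weeks for daily diary data: Week 9 is Days 57-63, Week 10 is 64-70, Week 11 is 71-77, and Week 12 starts on Day 78. Table 9.2-2 assigns the weekly questions (Constipation Severity, IBS Symptom Severity, Adequate Relief, Treatment Satisfaction) to those weeks by the day of the answer.

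In Table 9.2-2, Weeks 2 to 8 each have a seven-day window, ending with Week 8 at Days 53-59. The next row reads "Week 9 Day 60 Day 65". It is followed by Week 10 at Days 66-72, Week 11 at Days 73-79 and Week 12 from Day 80.

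The text below the table gives the rule: "In general, weekly questions will be assigned only to the analysis week for which the question covers at least 4 days of that week". It also says how repeat answers in one window are handled: "If patients answer the weekly questions multiple times for a week, for each question, the average of the respective answers will be assigned". A footnote extends the last window for some patients: "For patients completing the treatment period, but not entering the RW period, Day 87 defines the End study day for Week 12 assignment".

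One endpoint that depends on these assignments is defined in SAP section 7.9.3: "A 6/12 Week Adequate Relief Responder is a patient who reports Adequate Relief for at least 6 out of the 12 weeks".

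**The concern.** One row is a day short, the rows after it carry the shift forward, and no reason is given. The table and the rule beneath it then give different answers for the same data. A programmer who follows the table and one who follows the rule would derive different weekly values for the same patient.

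Two things can go wrong. A patient whose only Week 9 answer falls on Day 66 has no Week 9 value. And two answers that belong to different weeks can land in one window and be averaged. If both are Yes for Adequate Relief, two Yes weeks become one, so a patient with exactly 6 Yes weeks drops to 5 and is no longer a 6/12 Week Adequate Relief Responder.

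**Working it through.** **Inputs.** Analysis weeks from SAP Table 9.2-1: Week k = Days 7k-6 to 7k for k = 1 to 11, and Week 12 from Day 78. Answer windows from SAP Table 9.2-2. The recall period is the past 7 days (SAP section 5.3.3, for the severity and relief items; Treatment Satisfaction states no recall period but shares the windows). Weekly items are entered with the evening report (Protocol synopsis, Trial Procedures), so the day of the answer is taken as covered: Day d covers Days d-6 to d.

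**Rule as a formula.** Write d = 7k + j with j from 0 to 6. The answer covers 7 - j days of Week k and j days of Week k+1. At least 4 days of Week k requires 7 - j ≥ 4, so j ≤ 3. The window for Week k is therefore Days 7k-3 to 7k+3.

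**Reproducing the table.** For k = 2 this gives Days 11-17, and for k = 8 Days 53-59, both as printed; every row from Week 2 to Week 8 agrees. Week 1 starts at Day 7 because earlier answers reach into pretreatment and are discarded under the SAP's rule on answers that span phases; it ends at 7 + 3 = Day 10, as printed. From Week 9 the agreement breaks:

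| Week | By the rule | As printed |
|---|---|---|
| 9 | 60-66 | 60-65 |
| 10 | 67-73 | 66-72 |
| 11 | 74-80 | 73-79 |
| 12 | from 81 | from 80 |

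**The days that fail.**

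| Answer day | Days covered | Overlap | Filed under |
|---|---|---|---|
| 66 | 60-66 | Week 9: 4, Week 10: 3 | Week 10 |
| 73 | 67-73 | Week 10: 4, Week 11: 3 | Week 11 |
| 80 | 74-80 | Week 11: 4, Week 12: 3 | Week 12 |

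These are the only failures among the 87 - 7 + 1 = 81 report days from Day 7 to Day 87. With the corrected windows there are none.

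**Other recall reading.** The SAP's example says that "a weekly question answered on study day 2 would cover part of 1 day from the treatment phase" and 6 days from pretreatment. That fits recall ending the day before the answer (Days d-7 to d-1). Under it the printed table breaks the rule on 14 days: 11, 18, 25, 32, 39, 46, 53, 60, 66, 67, 73, 74, 80 and 81. The corrected table breaks it on 11, because 66, 73 and 80 drop out. Under this reading those three days cover only 2 days of the week to which the printed table assigns them.

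**Effect on usable weeks** (illustrative reporting patterns):

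| Pattern | As printed | Corrected |
|---|---|---|
| Days 7, 14, ..., 84 | 12 | 12 |
| Same, one answer 3 days late (66, 73 or 80) | 11; pair 66/70, 73/77 or 80/84 averaged | 12 |
| Days 10, 17, ..., 80; Week 12 ends Day 84 or 85 | 11 (Week 9 empty) | 11 (Week 12 empty) |
| Days 10, 17, ..., 87; Week 12 ends Day 87 or 88 | 11; pair 80/87 averaged | 12 |

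The last row can arise in two ways. One is the Day 87 footnote for completers who do not enter the RW Period. The other is an RW entrant with a late Week 12 visit: the visit window is Day 85±3, and Protocol section 7.5 says "Patients will take study drug as usual in the morning before the Week 12/ETP Visit", so the last dose can fall on Day 87 or 88. Of the seven possible regular seven-day cycles, only the one starting on Day 10 gives different results under the two tables.

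**The case against.** The short row itself is hard to dispute: the following rows run on from it without a gap, so it is not a text-extraction fault. The case on the other side is about weight.

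- **The rule is qualified.** It is stated to hold in general. That allows exceptions, but none is stated, and nothing distinguishes Week 9 from Week 8. This softens the conflict without explaining it.
- **The recall convention is inferred.** Counting the answer day is the reading that reproduces Weeks 1 to 8, but the SAP never states it, and its Day 2 example points the other way. This stands as a limit on the figure of 3 covered days. It does not rescue the table, since the same three days fail under both readings.
- **The harmful patterns are not shown to occur.** Seven-day steps from Day 1 give Days 8, 15, ..., 85, and the nominal cycle gives Days 7, 14, ..., 84; neither touches Day 66, 73 or 80. Protocol section 8.1.5 closes the evening report at midnight, and the documents do not say whether a missed weekly question stays open. This stands: the patterns are assumptions. The SAP's seven-day windows and repeat-answer rule do, however, provide for off-day answers.
- **Little depends on it.** This also stands. SAP section 7.9.3 says: "Additional efficacy endpoints will be explored outside of the formal testing procedures and not controlled for multiplicity". The primary and secondary endpoints use Table 9.2-1.

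A related gap is not relied on here: averaging a Yes (1) and a No (2) gives 1.5 for an item analysed as binary, and the SAP does not say how to treat it.

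**Conclusion.** The concern holds and is minor. Table 9.2-2 contradicts the SAP's own assignment rule on Days 66, 73 and 80. With the answer day counted as covered, those are the only 3 failures among 81 report days; with recall ending the day before, they are 3 of 14. Followed as printed, the table can leave a week empty, shift answers by a week or merge two answers, and in a borderline patient that can change the 6/12 Week Adequate Relief classification.

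The effect is confined to the additional endpoints built on weekly questions. The windows are identical in both arms, so no directional bias is claimed. How many patients answered on the affected days cannot be determined from the documents.

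**What to change.** In SAP Table 9.2-2, set Week 9 to Days 60-66, Week 10 to Days 67-73, Week 11 to Days 74-80, and start Week 12 on Day 81 with its existing end. That changes six cells: Week 9 end, Week 10 start and end, Week 11 start and end, and Week 12 start. The correction reduces the conflicts under both recall readings and needs no change to data collection. It should be made before unblinding, so that the choice between table and rule is not made with results in view.

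While the table is open, it would help to add a sentence stating which days an answer is taken to cover and to align the Day 2 example with it. A rule for repeat Adequate Relief answers in one window could be added at the same time, but the window correction does not depend on it.
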